7.3 Investigational Drug Product, Monitoring and Safety Procedures

7.3.1 Investigational Drug Product. The investigational drug product (LSALT peptide) will be supplied to the study site in aqueous solution at -20°C as a single concentration (1 mg/ml) in a glass vial with restricted access to the site pharmacist or designate. All four doses will be derived from the same formulation prior to patient administration. LSALT peptide vials will be single use only. Drug receipt/administration logs and temperature logs will be maintained by the study site using the Drug Accountability Form. The pharmacist/designate will ensure that the total number of vials in the drug dispatch log is present in the shipment from the sponsor. The pharmacist/designate will also ensure that there is no evidence of breakage of the drug vials. The CRO or sponsor must be notified immediately if any discrepancy is identified in the drug or temperature log or if any breakage occurs.

The LSALT peptide vial will be labeled in English and according to local regulatory requirements. The pharmacist or designate will be unblinded.

7.3.2 Drug Administration. LSALT peptide or an equivalent volume of 0.9% sodium chloride will be diluted in 0.9% sodium chloride solution to a volume of 100 ml mini-IV bag by an unblinded pharmacist or designate. The drug will be infused into the patient through a peripheral 18, 20 or 22 g intravenous catheter over 2 hours and under the supervision of the study investigator.

7.3.3 Pharmacy records. The principal investigator or a designate will be responsible for ensuring that the study site maintains an accurate record of the LSALT peptide inventory using the Drug Accountability Form. A coded label will be affixed to the patient CRF to identify placebo and LSALT peptide treated subjects.

7.3.4 Pretreatment Evaluation. 28 days prior to study initiation, enrolled participants will have a complete history and physical examination including vital signs, baseline fasting

laboratory studies (CBC, clinical chemistry), urinalysis, 12-lead electrocardiogram and chest x-ray (single PA view).

7.3.5 Safety Assessment. Patients will be monitored during drug administration and up to 3 weeks thereafter. Patients will be monitored for adverse effects using vital signs (seated, respiratory rate, heart rate, blood pressure, temperature and pulse oximetry), hematology, clinical chemistry, seated, supine single 12-lead electrocardiograms, chest radiography, and urine testing. Adverse events during the study will be reported and graded as per the CTCAE version 5.0.

7.3.6 Laboratory Testing. 25 mL of blood will be drawn for fasting laboratory assessment (hematology and clinical chemistries) at screening, baseline (pre-dose Day 1), and on study days 2, 4, and 7 (refer to Flow Chart). Additional bloodwork will be drawn at day 14 in the MAD cohort. In addition, 5 mL of blood will be collected for pharmacokinetic analysis at 30-minutes pre-dose, then 15, 30, 45, 60, 75, 90, 105, 120, 125, 130, 135, 140 minutes, and 3 hours from the onset of the LSALT infusion, 24 hours post drug administration on day 2 (from onset of 1st LSALT dose, SAD and MAD cohort), 72 hours post drug administration on day 4 (from onset of 1st LSALT dose, SAD and MAD cohort), and 96 hours post drug administration on day 7 (from onset of 3rd LSALT dose, MAD cohort). Participants will be required to have fasted from all food and drink except water for at least 8 hours prior to blood sampling.

Baseline hematology will include hemoglobin, hematocrit, total white blood cell count, white blood cell differentiation and platelet count. INR and PTT will also be performed. Clinical chemistry (fasting state) will include total protein, albumin, sodium, potassium, chloride, bicarbonate, random glucose, insulin, calcium, magnesium, phosphate, urea, uric acid, AST, ALT, ALP, LDH, TBili, GGT, creatinine, triglycerides, total cholesterol, and urinalysis (dipstick for protein, blood, glucose, ketones, pH, leukocytes and microscopic examination only if dipstick is not completely negative). Urinalysis will be conducted at the same times as the blood draws for hematology and clinical chemistries.

7.3.7 Women of Childbearing Potential. Women of childbearing potential (defined as women with regular menses, women with amenorrhea, women with irregular cycles, women using a contraceptive method that precludes withdrawal bleeding,) are required to have a negative serum pregnancy test (β -HCG) during screening and at the end of the study treatment.

Female and male participants (along with their female partners) are required to use a method of acceptable contraception, including one barrier method (condom) and one additional highly effective method (i.e., hormonal contraceptive, intra-uterine device) or abstinence for the duration of the study for 90 days following the last dose of study drug.

7.3.8 Duration of Follow-up. Participants are evaluated for adverse events for 72 hours and 6 days after receiving the low dose and single dose of study drug respectively. Patients receiving multiple daily dosing are evaluated for 17 days after receiving the last dose of the LSALT peptide. Participants with adverse events will be followed until resolution or stabilization of the adverse event. Follow-up after the conclusion of the study participation will be per routine clinical care.

8.0 DOSE ESCALATION AND STOPPING RULES

The first 4 participants will each receive a single low ascending dose of the LSALT peptide. Escalation of the dose in the next participant will occur at 72 hours if the prior participant experienced no adverse effects. The SRC will convene 24 hours after dosing of the last participant to determine if any changes in protocol design or SAD dosing are required. 96 hours following completion of this first low dose escalation phase, in the absence of adverse effects, participants in cohorts of 8 will be randomized 3:1 to receive the LSALT peptide or placebo. The dose for the first SAD cohort will be one intravenous infusion of 1.0 mg of LSALT peptide. The first 2 patients in each SAD cohort will be sentinels (1 treatment and 1 placebo). The SRC will convene 24 hours after dosing of the last sentinel patient to determine if any changes in protocol design or dosing are required. Sequential single dosing of LSALT peptide will occur as planned if sentinel participants show no clinical, biochemical or hematologic abnormalities. The SRC will convene 72 hours after dosing of the last participant to determine continuation of the single dose arm and next ascending dose cohort.

7 days following the completion of the SAD study arm, the SRC will convene to determine transition to the MAD study arm, the starting LSALT peptide dose and frequency. Entry into the multiple ascending dose arm will occur if no clinical, biochemical or hematologic abnormalities are observed at the SAD cohorts after 7 days. The starting dose of the MAD will consist of the 3 highest doses that caused no adverse effects in the SAD cohorts.

One adverse event (grade 3 or greater) in a participant or 2 moderate adverse events (grade 2) in the same cohort will result in a study pause and re-evaluation of the protocol. Termination of the trial will occur if 2 or more grade 3 or greater adverse events occur in the same cohort.

9.0 REGULATORY AND REPORTING REQUIREMENTS

9.1 Adverse Events (AEs)

Definition: Any untoward medical occurrence in a patient or clinical investigation subject administered a pharmaceutical product and which does not necessarily have to have a causal relationship with this treatment.

9.2 Severity (Intensity)

The descriptions and grading scales found in the revised NCI Common Terminology Criteria for Adverse Events (CTCAE) version 5.0 will be utilized for all toxicity reporting. A copy of the CTCAE version 5.0 can be downloaded from the CTEP website. Severity of AEs will be assessed as follows:

Grade 1 Mild; asymptomatic or mild symptoms; clinical or diagnostic observations only; intervention not indicated.

Grade 2 Moderate; minimal, local or noninvasive intervention indicated; limiting age appropriate instrumental activities of daily living.

Grade 3 Severe; Medically significant but not immediately life-threatening; hospitalization or prolongation of hospitalization indicated; disabling; limiting self-care activities of daily living.

Grade 4 Life-threatening consequences; urgent intervention indicated.

9.3 Assessment of Causality

All AEs (both serious and nonserious) will be assessed for relationship to investigational product by the Investigator. The investigator will assess the relationship of AEs to investigational product administration using the following categories:

Unrelated: The AE is clearly not related to the LSALT peptide and is clearly related to an underlying disease, environmental or toxic factor(s), or other drug/therapy.

Unlikely related: The AE does not follow a reasonable temporal sequence after LSALT peptide administration (eg, too soon or too long after investigational product or investigational product was not taken) and is plausibly related to an underlying disease, environmental or toxic factor(s), or other drug/therapy. For purposes of regulatory reporting, AEs classified as unlikely related will be considered unrelated to the LSALT peptide.

Possibly related: The AE follows a reasonable temporal sequence after investigational product administration but may be related to an underlying disease, environmental or toxic factor(s), or other drug/therapy. There is a reasonable possibility of a causal relationship between investigational product administration and the AE. For purposes of regulatory reporting, AEs classified as possibly related will be considered related to investigational product.

Probably related: The AE follows a reasonable temporal sequence after LSALT peptide administration and is unlikely to be related to an underlying disease, environmental or toxic factor(s), or other drug/therapy. The AE is consistent with the known response pattern of the LSALT peptide and may respond to stopping the LSALT peptide. For purposes of regulatory reporting, AEs classified as probably related will be considered related to the LSALT peptide.

Related: The adverse event is clearly related to the LSALT peptide; a re-challenge confirms the association (not required or desirable in some circumstances but provides strong evidence when it happens).

9.4 Expectedness

An unexpected adverse drug experience is defined as any adverse effect related to the investigational drug product, the specificity or severity of which is not consistent with the current investigator brochure (or risk information, if an IB is not required or available).

9.5 Serious Adverse Events (SAEs)

Each AE must be assessed and recorded in the eCRF as serious or not serious. Serious AEs must be reported as described in Section 7.9. International Conference on Harmonization Guidelines and the Code of Federal Regulations (CFR; 21 CFR 312.32, revised as of 01 April 2017). An SAE is defined as any adverse drug experience occurring at any dose that results in any of the following outcomes:

- Death;
- *A life-threatening adverse event;
- Inpatient hospitalization for at least 24 hours or prolongation of existing hospitalization;

- A persistent or significant disability/incapacity (i.e. substantial disruption of the ability to conduct normal life functions); or
- A congenital anomaly/birth defect.

Medical and scientific judgement should be exercised in deciding whether expedited reporting is appropriate in other situations, such as important medical events that may not be immediately life-threatening or result in death or hospitalisation but may jeopardise the patient or may require intervention to prevent one of the other outcomes listed in the definition above. *These should also usually be considered serious.*

*A life-threatening adverse event is defined as any adverse drug experience that places the participant (in the view of the investigator) at immediate risk of death from the reaction as it occurred, i.e., it does not include a reaction that, had it occurred in a more severe form, might have caused death.

9.6 Pregnancy

Should a female participant become pregnant or suspect she is pregnant while participating in this study, or should a male patient's partner become pregnant or suspect she is pregnant while the male is participating in this study, the treating investigator should be informed immediately. Female patients will be withdrawn from the study, and all pregnancies will be reported along the same timelines as a SAE. The Human Research Ethics Committee (HREC) and the sponsor will be informed. The participant will be asked to provide information on the outcome of the pregnancy, including premature termination should the case arise.

Spontaneous miscarriage and congenital abnormalities will be reported as SAEs. The follow-up period will be deemed to have ended when the health status of the child has been determined on its birth and followed up for 8 weeks following the birth for any potential abnormalities.

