6.0 PATIENT SELECTION

6.1 Inclusion Criteria

1. Adult participants aged 18-55 years (inclusive at the time of screening).
2. No prior history of major organ or systemic disease including diabetes, hypertension, kidney, heart or liver disease. Participants with childhood asthma are acceptable.
3. Normal hematology, clinical chemistry and urinalysis parameters at screening, unless not deemed clinically significant by the investigator.
4. Body Mass Index (BMI) between 18 kg/m² and 32 kg/m² (inclusive)
5. Taking no prescription medications 2 weeks prior to admission or over-the-counter medications 7 days prior to admission. Occasional use of paracetamol or ibuprofen (up to 1000 mg and 400 mg/day respectively) are acceptable. Routine vitamins and supplements are permissible at the discretion of the investigator.
6. Able to allow intravenous medication to be administered.
7. Males (along with their female partners) and females of childbearing potential (defined as a female who is not menopausal or surgically sterilized) must be willing to use an acceptable method of birth control during heterosexual activities including a condom and a second highly effective method (i.e., hormonal contraceptive, intra-uterine device) or abstinence for the duration of the study. Should a woman become pregnant or suspect she is pregnant while participating in this study, she must inform her treating physician immediately. Males and females should continue with the aforementioned contraception for 90 days after the last dose.
8. Able to understand and willing to sign an ethics committee-approved written informed consent document
9. Non-smokers. Social and light smokers of up to 10 cigarettes per day who can abstain from smoking during the confinement period and have no evidence of underlying lung disease (bronchitis, COPD or reactive airways disease).
10. Willing to remain abstinent from alcohol 24 hours prior to admission and until after the confinement period in the unit.

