6.2 Exclusion Criteria

1. A history of cardiovascular disease, diabetes or hypertension (Screening assessment >150/90 after 5 minutes sitting), significant neurological, pulmonary (including asthma), hepatic, rheumatic, autoimmune, haematological, metabolic or renal disorder.
2. Prescription medications are prohibited. No prescription medications 2 weeks prior to admission or over-the-counter medications 7 days prior to admission. Occasional use of paracetamol or ibuprofen (up to 1000 mg and 400 mg/day respectively) are acceptable. Routine vitamins and supplements are permissible at the discretion of the investigator
3. Any moderate or severe allergies, including anaphylaxis, to food, drugs or environmental allergens. Mild allergies such as hayfever may be included.
4. Females who are pregnant or lactating. Women of childbearing potential must have a negative pregnancy test within 14 days of study initiation and at baseline.

5. Consumption of caffeine 48 hours prior to start of study treatment and whilst confined to the unit.
6. History of any psychiatric illness or psychological disorder which may impair the ability to provide written informed consent or participate in the study
7. Clinically significant abnormal laboratory value at screening as determined by the Investigator.
8. Participant is sero-positive to HIV-1 or HIV-2, HCV or HBV.
9. History or presence of alcoholism within two years prior to the first study drug administration or drugs of abuse unless it can be explained to the satisfaction of the investigator that it is due to a standard dose of a prescribed medication and that an adequate wash-out will occur prior to admission as per inclusion #5
10. No findings on clinical examination that, in the opinion of the investigator, could compromise the safety of the participant or the results of the study.
11. Blood donation or significant blood loss within 60 days prior to the first study drug administration.
12. Administration of investigational product in another trial within 30 days prior to the first study drug administration or five half-lives, whichever is longer.
13. Surgery within the past 3 months prior to the first study drug administration determined by the PI to be clinically relevant.
14. Active malignancy or history of malignancy in the past 5 years

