1. PK blood samples: 5 ml of blood will be drawn at 30 prior to LSALT peptide infusion for baseline PK measurements. LSALT peptide infusion will begin and run over 2 hours. 5 ml of blood will be drawn at 15, 30, 45 60, 75, 90, 105, 120, 125, 130, 135, 140 (+/- 2 min) minutes, 3 hours (+/- 5 min) from the onset of the LSALT infusion
2. PK blood sample: 24 hours (+/- 30 mins) from the onset of the 1st infusion.
3. PK blood samples: 5 ml of blood will be drawn at 30 prior to LSALT peptide infusion. LSALT peptide infusion will begin and run over 2 hours. 5 ml of blood will be drawn at 15, 30, 45 60, 75, 90, 105, 120, 125, 130, 135, 140 (+/- 2 min) minutes and 3 hours (+/- 5 min) from the onset of the LSALT infusion
4. PK blood sample: 72 hours (+/- 30 mins) from the onset of the first LSALT infusion
5. PK blood sample: 96 hours (+/- 30 mins) from the end of the third LSALT infusion
6. Vital signs dosing day (seated): pre dose (+/-30 mins), 1 hour (+/- 10mins) , 2 hour (+/- 10 mins) 6 hours (+/- 15min) and 10 hours post completion of infusion (+/- 30 mins)
7. 12 lead electrocardiogram (supine): pre dose (+/- 30 mins), 2 hours (+/- 15 mins) and 8 hours post completion of infusion (+/- 30 mins)
8. Pregnancy test will be via serum B-hCG at Screening and a urine pregnancy test at pre dose (Study Day -1,) and follow up

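### The protocol asks for 90 days of contraception after the last dose, but its explicit duty to notify a pregnancy stops when participation ends, leaving 72 to 73 of those days uncovered in the remaining 5 mg MAD cohort

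*Protocol*

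**What the plan says.** **Contraception.** Inclusion criterion 7 (protocol 6.1) requires it during the study and then adds: "Males and females should continue with the aforementioned contraception for 90 days after the last dose". Section 7.3.7 repeats the 90 days in looser wording: "or abstinence for the duration of the study for 90 days following the last dose of study drug".

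**Notification.** Section 9.6 sets the trigger for women as "Should a female participant become pregnant or suspect she is pregnant while participating in this study". For a male participant's partner, the trigger is that she "become pregnant or suspect she is pregnant while the male is participating in this study". Inclusion 7 puts the same limit on a woman's own duty to report. Once notified, a pregnancy is reported on SAE timelines and followed to outcome, and the child is followed for 8 weeks after birth.

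**End of participation.** Section 7.3.8 gives adverse-event follow-up of 72 hours (low dose), 6 days (SAD) and 17 days after the last dose (MAD). It then says: "Follow-up after the conclusion of the study participation will be per routine clinical care".

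**Pregnancy tests.** Under 7.3.7, women of childbearing potential "are required to have a negative serum pregnancy test" during screening and again when study treatment ends. The MAD timetable footnote instead specifies, after a serum test at screening, "a urine pregnancy test at pre dose (Study Day -1,) and follow up". The low-dose and SAD footnotes also give urine at follow-up.

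**Status.** Section 3.7 reports the first six cohorts complete. Section 3.8 proposes a third MAD cohort at 5 mg daily for 3 days.

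**The concern.** The 90-day rule is the protocol's own statement of how long a pregnancy after dosing is to be avoided. A safety plan would normally collect pregnancies over at least that period. Here the duty to notify, and the outcome and infant follow-up that depend on it, are tied to participation, which is much shorter. A participant or partner who conceives on day 30 after the last dose falls inside the contraception window but is given no instruction in the protocol to tell the site, and the investigator has no stated duty to collect the outcome.

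This is a first-in-human study that admits women of childbearing potential and men with partners. A report of no pregnancies could be taken to cover the 90 days, when the protocol supports it only for the first days or weeks. The serum/urine conflict adds a smaller doubt about which end-of-study result the pregnancy listing will contain.

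**Working it through.** **Inputs.** Contraception window W = 90 days (inclusion 7; 7.3.7). Dose and last-visit days come from the procedures and timetables in 7.1.4 and 7.2.5: low dose, participant 1 on Day 1 and Day 4 (participant 4 on Day 13 and Day 16); SAD, Day 1 and Day 7; MAD, last dose Day 3 and last visit Day 21. Section 7.3.5 gives the longest monitoring period stated anywhere, up to 3 weeks.

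**Step 1: reproduce the stated follow-up.** F = last visit day − last dose day.

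- Low dose: 4 − 1 = 3 days (also 16 − 13 = 3). Matches the stated 72 hours.
- SAD: 7 − 1 = 6 days. Matches the stated 6 days.
- MAD: 21 − 3 = 18 days. Section 7.3.8 says 17, a one-day discrepancy. Counting from Day 4, the discharge day, gives 21 − 4 = 17.

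**Step 2: days with no explicit notification duty.** U = W − F, and share = U / W.

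| Part | F | U | Share of 90 days |
|---|---|---|---|
| Low dose | 3 | 87 | 96.7% |
| SAD | 6 | 84 | 93.3% |
| MAD, timetable | 18 | 72 | 80.0% |
| MAD, 7.3.8 | 17 | 73 | 81.1% |
| Longest period stated (7.3.5) | 21 | 69 | 76.7% |

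**Step 3: who is still affected.** Low dose (1) + SAD (3) + MAD (2) = 6 cohorts, which fits the six reported complete in 3.7. That leaves the 5 mg MAD cohort: 8 participants, 6 active and 2 placebo (protocol section 5.0; SAP 3.6). For them U is 72 to 73 days. The documents give no dosing dates, so the number of earlier participants still inside their 90 days cannot be counted.

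**Step 4: does another clause close the gap?**

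- The SAE timelines in 9.6 set how fast a pregnancy is reported, not how long the duty lasts.
- The SAE rule in 9.7 covers the clinical study or 1 day after dosing. It adds no 90-day period.
- The 8-week infant follow-up has no trigger of its own and starts from a pregnancy already notified.
- The last scheduled pregnancy test is at the final visit, and no later contact is planned.

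**Step 5: the tests.** Section 7.3.7 asks for serum at the end of study treatment, and the footnotes ask for urine at follow-up. In MAD the timing also differs: treatment ends on Day 3, but the only post-dose test is on Day 21.

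**The case against.** **Participation is not formally defined.** Section 7.3.7 runs the study duration and the 90 days together with no linking word, so it can be read as placing the 90 days inside the study. This stands as a drafting ambiguity. It does not rescue 9.6: inclusion 7 says contraception continues for the 90 days, and 7.3.8 places the end of participation earlier, with only routine care afterwards.

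**Some late events are already reportable.** Section 9.6 makes miscarriage and congenital abnormality SAEs, 9.7 requires SAEs during the clinical study to be reported, and section 17.0 ends the study at the last participant's last visit. For earlier cohorts that date lies beyond their own final visit. A pregnancy begun during participation but recognised later is arguably covered by 9.6. This is why the gap is described as no explicit duty to notify. A reader might infer that pregnancies will go unreported, but participants may volunteer them and the consent form may ask for them. For the final cohort, the end-of-study definition adds little.

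**Size.** A reader might apply the gap to all 52 participants: (4×87 + 24×84 + 24×72) / (52×90) = 4092/4680 = 87% of person-days. An amendment cannot reach most of that, because six cohorts are complete. The total also includes placebo recipients and any women not of childbearing potential. Few events are likely. Assuming 1 to 5% annual contraceptive failure (not in the documents) and counting all 8 participants, 8 × 72/365 × 0.01 to 0.05 = 0.02 to 0.08 expected pregnancies.

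**Exposure.** A reader might call a day-30 conception drug-exposed. The documents do not show this: the only half-life given is 0.66 to 1.17 hours, in rats. The point rests on consistency with the protocol's own window.

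**Exclusion 4.** It says "Women of childbearing potential must have a negative pregnancy test within 14 days of study initiation and at baseline". With screening open from Day -29, a reader might infer that some women are dosed without a recent test. They are not, because the pre-dose admission test (Day -1 in SAD and MAD) falls within 14 days.

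**Conclusion.** The mismatch is real and modest. For the remaining 5 mg MAD cohort of 8, the protocol sets no explicit duty to notify a pregnancy for 72 to 73 of the 90 days in which it requires contraception (80 to 81%). Most of the window is uncovered on every reading of follow-up length, from 76.7% upwards. The low-dose and SAD gaps of 87 and 84 days now matter only for anyone still within 90 days of dosing.

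This rests on reading participation as ending at the last scheduled visit, and on the six completed cohorts being low dose, three SAD and two MAD. It concerns the protocol only, since the consent form could not be checked. No endpoint depends on it: SAP 10.7 lists pregnancy data without summarising them. The serum/urine conflict is a separate, smaller inconsistency that also holds.

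**What to change.** In 9.6 and inclusion 7, replace the participation limit with the period from first dose until 90 days after the last dose. Apply it to female participants and to partners of male participants, with the existing SAE timelines, outcome collection and 8-week infant follow-up. Inclusion 7 names the treating physician as the recipient and 9.6 the treating investigator. Make these agree, so that a report made after the last visit reaches the site. Reword 7.3.7 so that the study duration and the 90 days are clearly two periods, and settle 17 against 18 days in 7.3.8. Check that the consent form matches, and tell anyone from earlier cohorts who is still inside their 90 days.

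Reconcile 7.3.7 with the timetable footnotes on the type and timing of the end-of-study pregnancy test.

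The cost is a few sentences across these sections and any matching consent text, with no added visits or tests. The downside is that the site must accept notifications for about 10 to 12 weeks after the last visit (72/7 = 10.3; 87/7 = 12.4). Capture still depends on self-report, so a later statement that no pregnancies were reported should say so.
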